7.0 CORRELATIVE/SPECIAL STUDIES

Samples will be collected for potential studies and will be stored in the laboratory of [name] in the Department of Leukemia at MD Anderson Cancer Center. Samples will be collected as follows:

Bone marrow aspirate: pre-therapy (within 28 days of study start), Day 28 of first cycle, and Day 28 of fourth cycle (or earlier if disease progression), and Day 28 of the fourth cycle of Part 2 (pacritinib + HMA).

Peripheral blood (including serum): on Days 0, 7, 14, 21 and 28 of the first cycle.

All samples can be obtained +/- 5 days.

Samples could be used, but not limited, to analysis of cytokine profile, genetic and epigenetic lesions and molecular characterization, and STAT3 phosphorylation.

Mutational profiling by the Molecular Diagnostics Lab (MDL) will be performed on pre-therapy and sequential bone marrow aspirates.

8.0 PATIENT EVALUATION

Pre-treatment

Results from tests performed as standard of care up to 28 days prior to study entry can be used for determining eligibility and establishing baseline measurements. Any clinically significant abnormal results (except for bone marrow aspiration) should be repeated within 48 hours of beginning therapy to establish a baseline.

- A complete history and physical exam including height, weight, and vital signs (blood pressure, heart rate, breathing rate, and temperature), disease documentation, and performance status (PS) should be performed 72 hours before initiation of study, and subsequently as indicated.
- Document significant baseline abnormalities and concomitant medications within 28 days of initiation of study.
- CBC, platelet count, creatinine, total bilirubin, AST and/or ALT, potassium and blood or urine pregnancy test (when indicated) should be performed 72 hours before initiation of study. Pregnancy testing will be conducted for any female that is of childbearing age that has not been surgically sterilized or without a menses for 12 consecutive months.
- Bone marrow aspirate and/or biopsy during the last 28 days preceding study initiation
- FLT3 and JAK2 mutational status (including FLT3 allelic ratio if mutation present). This can be performed on the pre-study bone marrow aspirate or from peripheral blood
- Cytogenetics will be obtained within 28 days prior to therapy, and should be repeated with all bone marrow assessments performed on study.
- EKG with documentation of QTc interval
- Echocardiogram or MUGA for evaluation of left ventricular ejection fraction
- Pretreatment correlative studies if patient signed for them during consent process.

During Treatment

- CBC, platelet count, creatinine, AST and/or ALT and total bilirubin weekly during first course of therapy, and prior to each course of therapy.
- Document adverse event assessment and concomitant medications at each clinic visit.
- EKG will be performed 4 hours post dosing on cycle 1 day 1 (+/- 1 hour) , on cycle 1 day 28 (+/- 5 days), cycle 4 day 28 (+/- 5 days), and as clinically indicated.
- Bone marrow aspiration on day 28 (+/- 5 days) of Cycle 1 and Cycle 4 of Part 1, and after

Cycle 4 of Part 2 (Pacritinib + HMA). Additional interim aspirations are allowed as indicated by the treating physician. If patients require the addition of a HMA prior to the end of cycle 4, a bone marrow aspiration prior to HMA start should be performed. Cytogenetic analysis should be performed for all bone marrow assessments.

- Peripheral blood for correlative studies as described above (+/- 5 days) and as shown in Table 8.

End-of-Treatment

Whenever possible, twenty-eight days following the last dose of study drug (+/- 7 days):

- CBC with chemistry
- Bone marrow aspirate, if clinically indicated.
- Document adverse event assessment and concomitant medications.

9.0 STUDY CALENDAR DURING

(all pretreatment tests within 28 days unless specified otherwise)

Table 8. Study Calendar

	Course 1					End of Treatment
	PreTx	W1	W2	W3	W4	
Complete history, physical exam including height, weight, vital signs, and PS	X	X				
Concomitant medication and significant baseline abnormality assessment	X	X	X	X	X	X
CBC ^{1,3}	X	X	X	X	X	X
Chemistries ³	X	X	X	X	X	X
Pregnancy test ³	X					
EKG and EF assessment by ECHO or MUGA	X	X			D28	
Bone marrow aspirate	X				D28	X ⁴

and/or biopsy with cytogenetics ²						
JAK2 and FLT3 mutational status ⁵	X					
Correlative Studies ⁶						

Footnotes:

PreTx, pretreatment; W, week; D day.

1 CBC includes complete differential and platelets;

2 Bone marrow aspirate and/or biopsy with cytogenetics should be performed within 28 days at pretreatment, on D28 (+/- 5 days) of Cycle 1 and Cycle 4, and D28 (+/- 5 days) of Cycle 4 after initiation of HMA agent + Pacritinib on Part 2. If HMA agent is added prior to end of Cycle 4, bone marrow aspirate and/or biopsy should be performed before prior to Part 2 start.

3 within 72 hours at pretreatment

4 if clinically indicated

5 mutational status can be assessed by peripheral blood or bone marrow as appropriate

6 Correlatives obtained during - Bone marrow aspirate sample: pre-therapy (within 28 days of study

start), Day 28 (+/- 5 days) of first cycle, and

Day 28 (+/- 5 days) of fourth cycle (or earlier if disease progression), and Day 28 (+/- 5 days) of the fourth cycle of Part 2

(pacritinib + HMA) Peripheral blood (including serum): on Days 0, 7, 14, 21 and 28 of the first cycle (+/- 5 days).

7 A single 12-lead EKG will be performed at screening, at 4 hours post dosing on cycle 1 day

1, on cycle 1 day 28 (+/- 5 days), cycle 4 day 28 (+/- 5 days), and as clinically indicated".

10.0 CRITERIA FOR RESPONSE

The primary endpoint is the overall response rate (ORR) per IWG-2006 criteria¹³. This is summarized in table 9 and 10. Response will include complete remission, partial remission, marrow complete remission and any hematological improvement achieved any time during the duration of the therapy.

Table 9. Proposed modified International Working Group response criteria for altering natural history of MDS⁷

Category	Response criteria (responses must last at least 4 wk)
Complete remission	Bone marrow: ≤5% myeloblasts with normal maturation of all cell lines

	
Persistent dysplasia will be noted[†]
 
Peripheral blood[‡]
 
 • Hgb ≥ 11 g/dL • Platelets $\geq 100 \times 10^9/L$ • Neutrophils $\geq 1.0 \times 10^9/L$[†] • Blasts 0%
Partial remission	
All CR criteria if abnormal before treatment except:
 
 • Bone marrow blasts decreased by $\geq 50\%$ over pretreatment but still $> 5\%$ • Cellularity and morphology not relevant
Marrow CR [†]	
Bone marrow: $\leq 5\%$ myeloblasts and decrease by $\geq 50\%$ over pretreatment[†]
 
Peripheral blood: if HI responses, they will be noted in addition to marrow CR[†]

Stable disease	
Failure to achieve at least PR, but no evidence of progression for > 8 wks

Failure	
Death during treatment or disease progression characterized by worsening of cytopenias, increase in percentage of bone marrow blasts, or progression to a more advanced MDS FAB subtype than pretreatment

Relapse after CR or PR	
At least 1 of the following:
 
 • Return to pretreatment bone marrow blast percentage • Decrement of $\geq 50\%$ from maximum remission/response levels in granulocytes or platelets • Reduction in Hgb concentration by ≥ 1.5 g/dL or transfusion dependence
Cytogenetic response	
Complete
 
 • Disappearance of the chromosomal abnormality without appearance of new ones 
Partial
 
 • At least 50% reduction of the chromosomal abnormality
Disease progression	
For patients with:
 
 • Less than 5% blasts: $\geq 50\%$ increase in blasts to $> 5\%$ blasts • 5%-10% blasts: $\geq 50\%$ increase to $> 10\%$ blasts • 10%-20% blasts: $\geq 50\%$ increase to $> 20\%$ blasts • 20%-30% blasts: $\geq 50\%$ increase to $> 30\%$ blasts 
Any of the following:
 
 • At least 50% decrement from maximum remission/response in granulocytes or platelets • Reduction in Hgb by ≥ 2 g/dL • Transfusion dependence
Survival	
Endpoints:
 
 • Overall: death from any cause • Event free: failure or death from any cause • PFS: disease progression or death from MDS • DFS: time to relapse

- Cause-specific death: death related to MDS

Table 10. Proposed modified International Working Group response criteria for hematologic improvement⁷

Hematologic improvement [*]	Response criteria (responses must last at least 8 wk) [†]
Erythroid response (pretreatment, < 11 g/dL)	Hgb increase by ≥ 1.5 g/dL Relevant reduction of units of RBC transfusions by an absolute number of at least 4 RBC transfusions/8 wk compared with the pretreatment transfusion number in the previous 8 wk. Only RBC transfusions given for a Hgb of ≤ 9.0 g/dL pretreatment will count in the RBC transfusion response evaluation [†]
Platelet response (pretreatment, < $100 \times 10^9/L$)	Absolute increase of $\geq 30 \times 10^9/L$ for patients starting with $> 20 \times 10^9/L$ platelets Increase from $< 20 \times 10^9/L$ to $> 20 \times 10^9/L$ and by at least 100% [†]
Neutrophil response (pretreatment, < $1.0 \times 10^9/L$)	At least 100% increase and an absolute increase $> 0.5 \times 10^9/L$ [†]
Progression or relapse after HI [‡]	At least 1 of the following: At least 50% decrement from maximum response levels in granulocytes or platelets Reduction in Hgb by ≥ 1.5 g/dL Transfusion dependence

Secondary endpoints include:

1. To evaluate efficacy of Pacritinib based on the presence of JAK2 and FLT3 mutations at diagnosis.
2. To evaluate efficacy based on IPSS, R-IPSS and LR-MDS risk classification systems at diagnosis.

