4.0 TREATMENT PLAN

Study Design

This is a Phase II study to evaluate the safety and efficacy of Pacritinib for the treatment of lower-risk MDS patients. The primary efficacy endpoint is the overall response rate (ORR) based on the IWG-2006 criteria, which includes complete remission (CR), partial remission (PR), and major hematologic improvement (HI). Patient's overall response will be assessed after 1 cycle of treatment but no more than after 4 cycles of treatment; cycle length is 28 days. If no response is attained after 4 cycles of treatment or if progression occurs during therapy at any time, the patient is eligible to continue on Pacritinib therapy with the addition of hypomethylating agent therapy (HMA) [Part 2]. A maximum total of 40 evaluable patients (n=40) will be enrolled.

Agent Administration

All patients will be registered through Protocol Data Management System (PDMS) or CORE.

One initial schedule of Pacritinib will be studied: 200 mg orally twice daily (every 12 hours) without regards to per oral (p.o.) intake. Study cycles will be administered every 28 days \pm 5 days or upon resolution of any clinically significant study drug related adverse event (AE) to grade 0-1, whichever occurs first.

Patients will receive the first course of therapy without interruption regardless of degree of myelosuppression unless patients with an un-transfused pre-treatment platelet count $\geq 50 \times 10^9/L$

$10^9/L$ drops to less than $10 \times 10^9/L$. In that case, drug will be held until platelets return $\geq 10 \times 10^9/L$ and resumed at the next lower dose if appropriate. If prolonged myelosuppression is observed with evidence of a hypocellular marrow (marrow cellularity less than 5% without evidence of recurrent MDS) drug will be stopped. Subsequent courses of Pacritinib will be given at the next lower dose, once counts recover. Count recovery will be considered if the ANC is $\geq 1 \times 10^9/L$ and platelets $\geq 50 \times 10^9/L$. For other clinical situations, subsequent courses of therapy will be administered at the discretion of the treating physician. Patients with residual disease may start the next cycle with neutrophil or platelet counts lower than these, if judged to be in the best interest of the patient to initiate the next cycle. The decision to treat should be documented in the patient's medical record.

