Patients will be assessed for disease response at the completion of 4 cycles of treatment. If there has been no response to therapy (i.e. stable disease per IWG-2006), or if disease progression is identified, patients will be eligible to continue on the study with the addition of 5-azacitadine or decitabine, with continuation of Pacritinib, in **Part 2** (Pacritinib + HMA). Patients responding to therapy will continue on Pacritinib monotherapy. Patients with disease progression prior to 4 cycles of Pacritinib are also eligible to initiate the Pacritinib + HMA study portion prior to the completion of 4 cycles. In these patients, disease assessment including bone marrow aspiration should be performed prior to the initiation of Part 2. Patients receiving Pacritinib + HMA will be re-assessed for disease response after 4 cycles of *combination* treatment on Part 2. Patients on pacritinib monotherapy in Part 1 who manifest disease progression at any time, including before or after completion of 4 cycles of treatment, can continue on study in Part 2 with the addition of a hypomethylating agent.

The addition of HMA should be initiated on Day 1 of the next Pacritinib treatment cycle whenever possible. HMA dosing and dosing adjustments should be performed according to the approved package insert, or at a dose of decitabine 20mg/m² IV over 1 hour for 5 days every 4 weeks and according to standard of care (see Section 5.0 for rules of dose reduction or delay).

Duration of Therapy

All patients must complete a screening visit, day 1 visits for each new cycle (+/- 5 days), end of treatment visit and whenever possible, an end of study safety visit 28 days after the last dose of Pacritinib (+/- 7 days).

Patients may remain on study for up to 12 months if the patient demonstrates clinical benefit and no excessive toxicity (i.e. no clinically significant study-drug related grade ≥ 3 toxicity). Patients who are experiencing clinical benefit beyond 12 months and have not experienced excessive toxicity may be eligible to continue therapy after discussion with the PI and the discussion documented in the patient's medical record. After the end of therapy and/or 30 days after your last dose of study drug, the study staff will follow your health status by phone call every 2 months (+/- 2 months) until you receive another cancer treatment.

Treatment is expected to continue until one of the following criteria applies:

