12.0 STATISTICAL CONSIDERATIONS

General Description

This is a Phase II open-label study designed to evaluate the efficacy and toxicity of Pacritinib as single agent (Part 1) and Pacritinib + HMA (Part 2) in subjects with lower-risk myelodysplastic syndrome. The primary efficacy outcome of both parts is the overall response rate (ORR) based mainly on hematologic improvement defined by IWG-2006 criteria, and which also includes complete remission (CR), partial remission (PR) and marrow complete remission. In Part 1, patient's overall response will be assessed after 1 cycle of treatment but no more than after 4 cycles of treatment; cycle length is 28 days. If no response is attained after 4 cycles of treatment or if progression occurs during therapy at any time, the patient is eligible to continue on Pacritinib + HMA (Part 2). Part 2 will not continue if Part 1 is stopped early. A maximum of 40 total evaluable patients (n=40) will be enrolled.

Study design: Part 1

The standard practice is to put these patients on observation, an ORR rate of about 15% is clinically relevant. The target ORR with the experimental treatment is 15%. The regimen of the Pacritinib will be considered worthy of further investigation if it elicits an increase in ORR to 15% with acceptable toxicity. A >15% therapy related non-hematological grade 3/4 toxicity rate is considered unacceptable. Thus, interim monitoring rules, assuming the prior distributions below, were constructed that meet the following two conditions,

- 1) Stop if $\text{Prob}\{p(\text{ORR}, E) < 0.15 \mid \text{data}\} > 0.975$, or
- 2) Stop if $\text{Prob}\{p(\text{TOX}, E) > 0.15 \mid \text{data}\} > 0.975$,

where $P(\text{ORR}, E)$ and $P(\text{TOX}, E)$ are the true ORR and toxicity rates for the Pacritinib, and $p(\text{ORR}, H)$ is the true ORR rate of the standard treatment. The first rule provides for stopping the study if the data suggest that it is unlikely (i.e., probability < 2.5%) that ORR rate of the Pacritinib treatment is greater than 15.0%. The second condition will stop the study early if excessive therapy-related non-hematological grade 3/4 toxicity (>15%) is highly probable (i.e., probability >97.5%) for the Pacritinib. Monitoring for toxicity and futility will not begin until 5 patients have been evaluated, and cohort size for future evaluations is 5.

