The monitoring rule for the toxicity rate, based on these assumptions and monitoring conditions above is found in Table 11. For example, accrual will cease if 4 or more patients experience toxicities among the first 5 patients.

Table 11. Stop accrual if the number of drug-related non-hematological grade 3/4 toxicities is greater than or equal to indicated (i.e., # patients with toxicities) among the number of patients evaluated								
# patients evaluated	5	10	15	20	25	30	35	40
# patients with toxicities	4-5	5-10	6-15	7-20	8-25	10-30	11-35	Always stop with this many patients

Monitoring the ORR rate, based on the above assumptions and monitoring conditions is found in Table 12. For example, accrual will cease if 0 patients experience an overall response within 4 cycles in the first 15 patients treated.

Table 12. Stop accrual if the number with overall response is less than or equal to indicated (i.e., # patients with overall response) among the number of patients evaluated					
# patients evaluated	5-10		15-25	30-35	40
# patients with overall response	Never Stop with this many patients		0	0-1	Always stop with this many patients

Multc Lean Desktop (version 2.1.0) was used to generate the toxicity and futility stopping boundaries and the OC table (Table 13). In order to utilize the software for the design, a response constant rate of 0.15 and beta (0.3, 1.7) priors were assumed for the standard treatment response distribution and experimental treatment response prior distribution, respectively. In addition, a 15% toxicity constant rate and beta (0.3, 1.7) priors were assumed for the standard treatment toxicity constant rate and experimental treatment toxicity prior distribution, respectively.

The probability of stopping the study early if the true ORR of the Pacritinib was 15% and the true toxicity rate was 15% was 21.9%. Probabilities of stopping early for high true toxicity rates (i.e., 40%) were 95.3% when the true ORR was 15%, and 94.4% when true ORR rate was 30%.

Table 13. Operating characteristics for simultaneous monitoring response and toxicity rates for patients treated with Pacritinib treatment

True Toxicity Rate	True ORR	Prob(stop the trial early)
0.05	0.05	0.6908
	0.10	0.3528
	0.15	0.1654
	0.20	0.0754
	0.25	0.0338
	0.30	0.0150
0.10	0.05	0.6944
	0.10	0.3603
	0.15	0.1750
	0.20	0.0861
	0.25	0.0450
	0.30	0.0264
0.15	0.05	0.7109
	0.10	0.3947
	0.15	0.2194
	0.20	0.1352
	0.25	0.0964
	0.30	0.0787
0.20	0.05	0.7533
	0.10	0.4836
	0.15	0.3341

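### The Part 1 primary response rate has conflicting components and time windows, and its drop-out rule can turn a documented responder into a failure

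*Combined protocol and SAP*

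**What the plan says.** **Components.** Section 4.0 (Study Design) describes the overall response rate (ORR) as one "which includes complete remission (CR), partial remission (PR), and major hematologic improvement (HI"). Section 10.0 states that "Response will include complete remission, partial remission, marrow complete remission and any hematological improvement achieved any time during the duration of the therapy". Section 12.0 (General Description) bases ORR mainly on "hematologic improvement defined by IWG-2006 criteria, and which also includes complete remission (CR), partial remission (PR) and marrow complete remission". Table 10 in Section 10.0 defines erythroid, platelet and neutrophil improvement, each lasting at least 8 weeks, and has no *major* grade.

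**Window.** Sections 4.0 and 12.0 both say that "overall response will be assessed after 1 cycle of treatment but no more than after 4 cycles of treatment". The worked futility example under Study design: Part 1 uses the same window: "accrual will cease if 0 patients experience an overall response within 4 cycles in the first 15 patients treated". Section 10.0 ties its window to the duration of therapy, and Section 4.0 (Duration of Therapy) says: "Patients may remain on study for up to 12 months if the patient demonstrates clinical benefit and no excessive toxicity". Treatment may go on longer after discussion with the principal investigator.

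**Drop-outs.** The Statistical Analysis Plan in Section 12.0 treats patients who leave before completing all the cycles as failures in the primary analysis. It does not say how many cycles that is, and it makes no exception for a patient whose response is already on record. It then adds that ORR during the study period will also be presented.

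**The concern.** The primary endpoint of a single-arm phase II trial should give the same responder count whoever applies it. Here three choices are left open.

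- A patient whose only response is marrow complete remission counts under Sections 10.0 and 12.0 but not under Section 4.0.
- A first response on pacritinib alone after cycle 4 counts under Section 10.0 but not under Sections 4.0 and 12.0.
- A responder who leaves early can be a failure under the drop-out rule. Section 11.0 lists possible transplant, adverse events, intercurrent illness and patient request as reasons for removal, so a patient in remission who leaves for transplant could be coded a failure.

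The trial is open-label, so an unresolved choice could be made after results are known. Interim decisions are exposed too. Table 12 stops accrual at 0 responders among 15, 20 or 25 patients, so one patient with marrow remission only can separate stopping from continuing, and "Part 2 will not continue if Part 1 is stopped early".

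Responses after a hypomethylating agent (HMA) is added are not part of the problem. Section 12.0 separates "Pacritinib as single agent (Part 1) and Pacritinib + HMA (Part 2"), and it estimates the two rates separately.

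**Working it through.** **1. The three texts side by side (Part 1)**

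| | Section 4.0 | Section 10.0 | Section 12.0 |
|---|---|---|---|
| Complete or partial remission | yes | yes | yes |
| Marrow complete remission | no | yes | yes |
| Hematologic improvement | *major* only (undefined) | any | as defined by IWG-2006 |
| Window | up to 4 cycles | any time on therapy | up to 4 cycles |

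Window lengths: 4 × 28 days = 16 weeks, against up to 12 months, or 365/28 = 13.0 cycles.

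**2. What one patient is worth.** 1/40 = 2.5 points. Exact (Clopper-Pearson) 95% intervals:

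| Responders | ORR | 95% CI |
|---|---|---|
| 5/40 | 12.5% | 4.2–26.8% |
| 6/40 | 15.0% | 5.7–29.8% |
| 7/40 | 17.5% | 7.3–32.8% |

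**3. The plan's own figures first.** A beta(0.3, 1.7) prior, a 15% reference rate and a 0.975 cutoff, with looks every 5 patients, reproduce the boundaries exactly:

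- Table 12 (futility): stop at 0 responders at 15, 20 and 25 patients, and at 0–1 at 30 and 35.
- Table 11 (toxicity): stop at 4, 5, 6, 7, 8, 10 and 11 toxicities at 5, 10, … 35 patients.

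Exact binomial calculation through those looks gives:

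- P(futility stop) = 0.1076 at ORR 15% and 0.2765 at ORR 10%.
- P(toxicity stop) = 0.0056, 0.0443 and 0.1623 at toxicity 10%, 15% and 20%.
- P(early stop) at ORR 15% and toxicity 15%, independent = 1 − (1 − 0.1076)(1 − 0.0443) = 0.147.

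Section 12.0 prints 21.9% for that last cell, so this figure is **not** reproduced. That is a separate matter from the definitions; step 6 shows how little it affects what follows.

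**4. Illustration of the drop-out rule.** The plan states no responder count for success, so 15% is read here as at least 6 of 40. True ORR is 15%. A fraction *f* of responders is recoded as failures at the final analysis, so the counted rate is 0.15(1 − *f*). The quantity is P(reach 40 patients and count at least 6): the Table 12 result multiplied by the chance of no toxicity stop.

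| *f* (assumed) | Counted ORR | Table 12 alone | Both rules, toxicity 15% | [toxicity 10%, 20%] |
|---|---|---|---|---|
| 0 | 15.0% | 55.3% | 52.9% | [55.0%, 46.3%] |
| 10% | 13.5% | 44.9% | 42.9% | [44.6%, 37.6%] |
| 20% | 12.0% | 34.0% | 32.5% | [33.8%, 28.5%] |
| one third | 10.0% | 20.3% | 19.4% | [20.2%, 17.0%] |

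Example, *f* = 0: 0.5532 × (1 − 0.0443) = 0.529.

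**5. Illustration of the window.** ORR within 4 cycles is 10%. A fraction *L* of window non-responders first respond later on pacritinib alone, so the counted rate is 0.10 + 0.90*L*.

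| *L* (assumed) | Counted ORR | Table 12 alone | Both rules, toxicity 15% | [toxicity 10%, 20%] |
|---|---|---|---|---|
| 0 | 10.0% | 19.9% | 19.0% | [19.8%, 16.7%] |
| 2% | 11.8% | 30.9% | 29.6% | [30.8%, 25.9%] |
| 5% | 14.5% | 46.6% | 44.5% | [46.3%, 39.0%] |

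**6. Sensitivity to step 3.** With looks after every patient from the fifth, early stopping at 15%/15% is 26.6%, which lies on the other side of the printed 21.9%. The drop-out series becomes 48.5%, 39.6%, 30.2% and 18.2%: the same pattern.

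**The case against.** The best reply is that Section 12.0 already settles most of this. Its components match Section 10.0, its window matches Section 4.0 and the futility example, and its separate study-period ORR is a natural home for the any-time wording. A monitor using the definition in the section that holds the stopping rules would count marrow remission. This is a fair account of what was probably meant. It does not remove the conflict: Section 10.0 attaches the any-time window to the primary endpoint by name, and no text gives precedence. The drop-out rule also sits inside Section 12.0 and stays undefined there.

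Second, few late monotherapy responses should arise. Non-responders are offered an HMA, staying on study depends on clinical benefit, and Part 1 marrows are scheduled only at cycles 1 and 4. That limits the size. But Section 4.0 makes non-responders eligible for an HMA and does not say it is required, so the group need not be empty.

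Third, failing drop-outs is ordinary conservatism, and the only fixed Part 1 count is 4 cycles. On that reading few responders are affected, because an 8-week improvement must be reached, sustained and followed by departure before week 16. Conservatism is a sound reason to fail patients without a response; the rule as written is not limited to them.

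Finally, the recoding and late-response fractions have no source in the documents, at least 6 of 40 is not a rule of the plan, and the one-patient intervals overlap widely. All of that stands. The probabilities show sensitivity and are not predictions.

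**Conclusion.** The concern holds. The components differ between Section 4.0 and Sections 10.0 and 12.0, the window in Section 10.0 contradicts the 4-cycle window used elsewhere, and the drop-out rule has neither a cycle count nor an exception for documented responders. These are defects of text and need no assumption.

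Their certain size is 2.5 percentage points per reclassified patient against a 15% target. What moves is the point estimate, since the intervals overlap. The larger effects in the two illustrations depend on assumed fractions, on reading 15% as at least 6 of 40, and on response and toxicity being independent. The point should be fixed before analysis; it does not undermine the design.

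**What to change.** Use one definition in Sections 4.0, 10.0 and 12.0: Part 1 primary ORR is complete remission, partial remission, marrow complete remission or hematologic improvement per Tables 9 and 10, with onset on pacritinib alone within 4 cycles.

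- Section 4.0: delete *major* and add marrow complete remission.
- Section 10.0: remove the any-time wording from the primary definition.
- Statistical Analysis Plan: replace the reference to all the cycles with the 4-cycle window, and count as failures only drop-outs without a documented response in it. Keep study-period ORR as supportive; late monotherapy responses belong there.
- State whether an improvement that begins in the window may complete its 8 weeks after cycle 4, and apply the same rule at the futility looks.
- Reconcile the Section 4.0 description of no response as stable disease with the ORR components. Table 9 defines stable disease as failure to achieve at least partial remission, so a patient with hematologic improvement only could fit both. No treatment rule is proposed here.

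Cost: a wording amendment with no new patients or visits. It uses the blood counts already taken before each course (Section 8.0) and the transfusion data Table 10 already needs. The downside is that late monotherapy responses count only in the supportive analysis.

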3.0 PATIENT SELECTION

Inclusion criteria

1. Signed informed consent indicating that patients are aware of the investigational nature of this study, in keeping with the policies of MDACC, must be obtained prior to any study specific procedures.
2. Patients with a histologically confirmed diagnosis of MDS by World Health Organization (WHO) classification and lower-risk MDS as defined by the IPSS classification² (Low or Int-1 disease) or R-IPSS classification¹² (Very Low or Low) are eligible. Patients with MDS/MPD overlap syndromes including CMML are also eligible if they have Low or Int-1 disease per IPSS. Patients may have received MDS-directed therapy (i.e. lenalidomide), although patients with prior exposure to hypomethylating agents (e.g. 5-azacitidine or decitabine) are not eligible.
3. The interval from prior treatment to time of study drug administration is at least 1 week (except for hydroxyurea or steroid therapy) with recovery from all prior therapy-related toxicities
4. Age ≥ 18 years old.
5. Eastern Cooperative Oncology Group (ECOG) performance status of 0 to 2.
6. Adequate liver function, as evidence by serum bilirubin $\leq 2x$ the laboratory normal range (except for patients with Gilbert's Disease), or an aspartate aminotransferase (AST) or alanine aminotransferase (ALT) of $\leq 2.5x$ the upper limit of normal (ULN) or $\leq 5x$ ULN if hepatic disease involvement is present as determined by the investigator.
7. Serum creatinine (Cr) $\leq 2x$ ULN or 24-hour creatinine clearance ≥ 50 ml/min
8. Subjects of reproductive potential must agree to the use of acceptable contraceptive methods for the duration of the time on study and a further 6 months after completion of treatment. Women of childbearing potential must have a negative blood or urine pregnancy test within 72 hours of start of treatment.

Exclusion criteria

1. Subjects with any prior exposure to the hypomethylating agents (5-azacitidine or decitabine) are excluded.
2. Subjects with any prior exposure to JAK2 inhibitor therapy (i.e. ruxolitinib or prior pacritinib therapy) are excluded.

3. Any prior or coexisting medical condition that in the investigator's judgment will substantially increase the risk associated with the subject's participation in the study.
4. Psychiatric disorders or altered mental status precluding understanding of the informed consent process and/or completion of the necessary study procedures.

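### Marrow CR counts toward the primary ORR with no baseline blast requirement, so a small sustained fall in a low-blast patient scores as a response, and the 4-week rule cannot be checked for falls first seen at Cycle 4 Day 28

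*Combined protocol and SAP*

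**What the plan says.** The three statements of the primary endpoint differ on this component.

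- Section 10 (Criteria for Response): "Response will include complete remission, partial remission, marrow complete remission and any hematological improvement", reached at any point while on therapy.
- Section 12 (General Description) bases ORR mainly on hematologic improvement, "and which also includes complete remission (CR), partial remission (PR) and marrow complete remission".
- Section 4 (Study Design) describes the same ORR as one "which includes complete remission (CR), partial remission (PR), and major hematologic improvement (HI"), without marrow CR.

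The marrow CR row of Table 9 asks for at most 5% "myeloblasts and decrease by" at least 50% over pretreatment. No blood-count change is needed; HI is only noted alongside. The table's column header adds "responses must last at least 4 wk".

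Inclusion criterion 2 in Section 3 admits "lower-risk MDS as defined by the IPSS classification" (Low or Int-1), or R-IPSS Very Low or Low, and sets no blast minimum. Section 8 schedules "Bone marrow aspiration on day 28 (+/- 5 days) of Cycle 1 and Cycle 4 of Part 1", allows extra aspirations at the physician's discretion, and schedules one on-treatment marrow in Part 2, after Cycle 4.

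**The concern.** Marrow CR is meaningful when there are excess blasts to clear. Neighbouring rows have an entry condition that marrow CR lacks: PR requires blasts still above 5%, and each HI line in Table 10 has a pretreatment threshold. In a patient who starts at or below 5%, the level condition is already met, so the whole response rests on a relative fall in a very small number. Such a fall can come from counting error.

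Part 1 is uncontrolled and has a target ORR of only 15%. Table 12 stops accrual on 0 responses among 15 to 25 patients, or at most 1 among 30 or 35, so one or two false responses can disarm it. Under Section 4, response status also decides whether a patient stays on monotherapy or becomes eligible for Part 2.

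**Working it through.** **Step 1: the population.** In Table 1 only blasts below 5% score 0, so every IPSS Low patient (total score 0) starts below 5%. In Table 2, Low is 267/(267+314) = 46% of Low plus Int-1. That is a floor for the share below 5% in that cohort, since Int-1 may have under 5% or 5-10% blasts. The documents do not give the split.

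**Step 2: the duration rule.** The two scheduled Part 1 marrows are three cycles apart (3 × 28 = 84 days), so a fall seen at Cycle 1 Day 28 can be checked at Cycle 4 Day 28. A fall first seen at Cycle 4 Day 28 has no later scheduled Part 1 marrow.

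**Step 3: false marrow CR from counting error.** Assumptions: true blast fraction p is unchanged; M = 200 or 500 cells are counted; readings are independent binomial counts. With baseline count X and follow-up count Y, both Bin(M, p):

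q(one) = sum over x from 1 to 0.05M of P(X = x) · P(Y ≤ x/2).

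For two marrows, P(Y ≤ x/2) = F is replaced inside the sum by 1 − (1 − F)² for either, or by F² for both. As an illustration, take M = 200 and p = 2%. A baseline of 4 cells reads 2%, and a follow-up of 2 cells or fewer qualifies, with probability 0.235. Summing over all baselines gives:

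| True blasts | One marrow (200/500) | Either of two | Both |
|---|---|---|---|
| 1% | 32% / 18% | 49% / 31% | 15% / 6% |
| 2% | 22% / 8% | 36% / 15% | 7% / 1.5% |
| 3% | 13% / 4% | 23% / 7% | 3% / 0.4% |
| 4% | 6% / 1% | 11% / 2% | 0.6% / 0% |

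These rates apply to low-blast patients. For a whole trial, assume 46% at 2% and 54% at 7%. With 200 cells and both marrows required, the rate is 0.46 × 7.4% + 0.54 × 0.4% = 3.6%. Across 200 or 500 cells, with or without whole-percent rounding, this mix gives 0.7-3.9%. A mix of 75% at 2% and 25% at 7% gives 1.1-6.1%.

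**Step 4: the futility rule.** The plan's boundaries come first. With the Beta(0.3, 1.7) prior, Pr(ORR < 0.15) is 0.973 at 0/10 and 0.990 at 0/15; it is 0.973 at 1/25 and 0.987 at 1/30. Against the 0.975 cut-off this reproduces Table 12. Exact recursion over looks at 5, 10, ..., 35 gives a futility stopping probability of 0.633 at a true ORR of 5%. Table 13 prints 0.6908 for ORR 5% and toxicity 5%; that value is reproduced with looks every 4 patients, not the stated 5. This is a separate matter, and the figures below use the printed rule.

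If false marrow CRs occur at rate q independently of true response, the apparent ORR is 0.05 + 0.95q:

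| q | Apparent ORR | P(futility stop) |
|---|---|---|
| 0 | 5.0% | 0.63 |
| 1.5% | 6.4% | 0.51 |
| 4% | 8.8% | 0.34 |
| 6% | 10.7% | 0.24 |
| 10% | 14.5% | 0.12 |

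**Step 5: effect of requiring baseline blasts above 5%.** The sum now runs over x > 0.05M, with follow-up at most 5% and at most x/2. At one unconfirmed marrow the false rate (200/500 cells) is 0.2%/0.0% at true 2% and 3.9%/0.2% at true 7%. It is 5.2%/1.0% at true 4%, where some baselines are misread as above 5%.

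**The case against.** The plan adopts criteria that it cites as IWG-2006, and those criteria carry a 4-week duration requirement. Three stronger readings are tempting, and the documents do not support them.

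- *Any single reading of 2% falling to 1% is a response.* It is not: Table 9 requires the response to last. The both-marrows column is the closest proxy for that rule.
- *The enrolled population is mostly below 5% blasts.* The documents do not say so. They support a 46% floor in the Table 2 cohort. R-IPSS entry and overlap syndromes including CMML add further uncertainty.
- *Counting noise alone approaches the 15% target.* That needs unconfirmed or either-marrow scoring, or true 1% blasts with 200 cells. Under confirmation, the mixed-population rates are about 1-6%.

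Two further limits stand. The two-marrow figures apply to Part 1 only, because Part 2 schedules a single on-treatment marrow. The marrow CR row also carries footnote markers whose text is not visible in the extract, so a qualifier there cannot be ruled out.

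These objections reduce the size of the problem but do not remove it. The written definition still accepts a sustained fall within the low-blast range. Section 8 permits an extra aspiration but does not require one to confirm a late fall. Even confirmed-range noise weakens the futility rule materially.

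**Conclusion.** The concern holds in limited form. As written in Sections 10 and 12, marrow CR can be earned by patients who had no excess blasts to clear, and part of the duration rule is not checkable on the planned schedule. False rates of 1.5-6%, roughly the range if both marrows must qualify, cut futility stopping at a true ORR of 5% from 0.63 to between 0.51 and 0.24. A 10% rate, which needs looser scoring in these mixes, cuts it to 0.12.

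The sizes rest on assumed cell counts, unchanged true blasts, independent binomial readings and an assumed blast mix. The gap in the definition and the conflict with Section 4 need none of these. Severity: should fix.

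**What to change.** In Section 10 (Table 9 and the sentence above it) and Section 12, count marrow CR toward ORR only when pretreatment marrow blasts are above 5%. For patients at or below 5%, report blast changes descriptively; CR and HI still count. Use the same definition for the response counts entered in Tables 12 and 15. Reconcile the ORR definition in Section 4 with Sections 10 and 12, so that one list of components applies throughout. It would also help to state how the 4-week duration is established for a marrow CR first seen at Cycle 4 Day 28.

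The baseline restriction takes a sentence in each section and needs no new data. Its cost is that the reported ORR may be lower. It does not remove misclassification in patients whose true blasts lie just under 5%.
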